#### 4. Study Procedures

##### a. Study design, including the sequence and timing of study procedures (distinguish research procedures from those that are part of routine care).

All procedures will be conducted solely for study purposes. We will conduct a cross-sectional observational study in 40 patients for the R61 phase. 20 patients will have latent PSSP with non-painful restriction in passive shoulder ER-ROM in their paretic arm, and 20 will have active PSSP with painful ( $\geq 5/10$ ) restriction in passive shoulder ER-ROM as defined above. All 40 subjects will also undergo testing on their non-paretic arm which will serve as a proxy for “healthy” control. All subjects will undergo ***3 types of quantitative imaging of the pectoralis major (key internal rotator) and infraspinatus (key external rotator) muscles of both arms:*** (1) 3-D T1ρ MRI to quantify the extent of HA accumulation (primary outcome for Aim 1), (2) Quantitative US statistical echo texture mapping (secondary outcome for Aim 1), and (3) Quantitative US shear strain mapping to distinguish between latent and active PSSP on the paretic side compared with the non-paretic side (primary outcome for Aim 2).

After obtaining informed consent, subjects will be screened to ensure that they meet inclusion-exclusion criteria. They will then undergo the following clinical and imaging assessments.

**Clinical Assessments:** All clinical assessments will be performed on both arms and be used to correlate with the imaging measures.

Date: August 28, 2023

Principal Investigator: [name]

Application Number: IRB00354876

Passive ROM in the upper limb will be measured at the shoulder (flexion-extension, abduction-adduction, internal and external rotation) in the standard sagittal, horizontal and coronal planes using video and/or 3-D motion capture techniques (Motion Monitor, Innovative Sports Training, Inc., Chicago, IL) [82]. This system uses the trackSTAR 800 sensor (Ascension Technology Corp., VT) that has a static resolution of 0.5 mm for position and 0.1° for angular orientation [83]. During passive ROM, we will also assess muscle stiffness with the Modified Ashworth Scale [84] to determine the degree of resistance [85].

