**Equation 1**

$$S = A \cdot e^{-TSL/T_{1\rho}} + A_0$$

**MRI Data Analysis:** The mean values and standard deviations of T1 $\rho$  relaxation times (ms) will be obtained from the defined regions of interest in the pectoralis major and infraspinatus muscles and will be compared on the paretic and non-paretic sides using mixed model analysis wherein the two sides are nested within one person, and healthy (non-paretic) versus latent PSSP versus active PSSP are examined as fixed effects. Prior to final analysis we will perform model diagnostics to assure that model assumptions regarding the fixed and random effects are met. The mean water and fat fractions of the muscles will also be obtained in percentages to quantify fat infiltration in the muscles, which will be used as predictors in the analysis. We will use Pearson's correlations to correlate the clinical and imaging measures.

**Expected results, potential pitfalls & solutions:** We expect an increase in T1 $\rho$  relaxation times in the paretic pectoralis major and infraspinatus muscles compared with the non-paretic side. We may also see a difference in location of the signal and/or relaxation times between latent and active PSSP. For example, subjects with active PSSP may show higher relaxation times in the

epimysial regions as seen with overuse injury, whereas subjects with latent PSSP may show higher relaxation times in the perimysial region. A two-compartment model of T1ρ mapping (bi-exponential model) can separate out the signal from the GAG content and the free water content of the ECM, and delineate a clearer picture of the extracellular environment of the muscle [23]. We can also analyze the data collected using this model, which may differentiate latent from active PSSP.

[figure not shown]
***All the MRI data will be collected and analyzed in collaboration with co-I [name] at Johns Hopkins in conjunction with [name] at NYU Langone.***

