**US Data Processing:** US data acquired from the non-paretic and paretic sides will be processed with a custom program written in Matlab (Natick, MA). Tissue displacements between successive US frames will be estimated from the “raw” US radio frequency (RF) data using cross-correlation techniques [101, 102] with a 1 mm window incremented with a 90% overlap. The term “US frame” refers to the RF data acquired at each time point in the cine-loop. Tissue lateral displacement will be computed for each successive pair of US frames in a  $1 \times 1.5$  cm ROI centered laterally on the midpoint of the image. To visually document the presence of a shear plane within the muscle, we will generate successive displacement maps as a spatial representation of the displacement within the ROI for each pair of US frames. Corresponding cumulative lateral displacement maps will be obtained by summing tissue displacements over time. To calculate the magnitude of shear deformation at a standardized location across subjects, we will use a reference echolucent plane that is relatively stable during the movement and define sub-ROIs each  $2 \text{ mm} \times 10 \text{ mm}$  for analysis. The maximum shear strain in the sub-ROIs will be averaged and used for statistical analysis.

**US Data Analysis:** The mean values and standard deviations of the maximum shear strain will be obtained from the defined regions of interest in the pectoralis major and infraspinatus muscles and will be compared for latent and active PSSP on the paretic and non-paretic sides using mixed model analysis, as described above for Aim 1. We will use Pearson’s correlations to correlate the clinical and imaging measures.

**Expected results, potential pitfalls & solutions:** We expect that the mean maximum shear strain will be statistically significant between the healthy (non-paretic) and paretic latent and active PSSP groups to proceed to the R33 phase. We will have twice as much data for the non-paretic arm than for the latent and active PSSP groups. Since some subjects with stroke may not have perfectly healthy non-paretic sides, we will use the data from the healthiest subjects based on their clinical testing, which may provide a greater separation between these groups. ***The quantitative US data will be collected and analyzed in collaboration with Co-I [name] at Johns Hopkins with Co-I [name] at George Mason University.***

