**c. Statistical plan including sample size justification and interim data analysis.**

We determined our sample size for the R61 Phase based on the more stringent sample size requirement for Aim 2, which will compare two independent groups, i.e., patients with latent PSSP vs. patients with active PSSP in the paretic arm. Because Aims 1 and 2 have different measurements, we present our power analysis in terms of standardized effect sizes (Cohen's d), which would be applicable to either measurement (26).

Langevin et al's data on shear strain mapping in patients with and without low back pain (LBP), showed that the shear strain was reduced in the LBP group ( $56.4\% \pm 3.1\%$ ) compared with the No-LBP group ( $70.2\% \pm 3.6\%$ ), i.e., an extremely large effect size of 3.8, suggesting that large effect sizes are biologically plausible.

The effect sizes in Bishop et al's follow up porcine study (83), showed equally large effect sizes comparing shear strain in control animals versus animals with restricted movement (similar to latent PSSP in our study), versus animals with restricted movement plus injury (similar to active PSSP in our study). We conservatively assume a Cohen's d of 1, which though large is not as large as the cited numbers. To detect a difference between latent PSSP versus active PSSP, a sample size of 17 per group is adequate for statistical significance at the 0.05 level with 80% power. For comparisons between paretic versus non-paretic shoulders, we expect greater power for within-person paired comparisons. However, conservatively assuming no advantage due to within-person correlations, we will also have 80% power to detect differences between latent PSSP versus healthy (non-paretic) shoulders and active PSSP versus healthy shoulders (non-paretic). Since we will be making multiple MRI and US measurements in a population that is disabled and in pain, it is possible that there will be some attrition. Hence accounting for 15% attrition, we will enroll 20 patients per latent PSSP and active PSSP group.

**Figure 10.** Overview of study design for the R61 Phase.

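### Aim 2 compares paretic arms with a selected, undefined set of the healthiest controls, which can bias the healthy-versus-latent and healthy-versus-active contrasts; the primary analysis should keep every available non-paretic arm

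*Combined protocol and SAP*

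**What the plan says.** The selection appears in Section 4a, Aim 2, in the paragraph on expected results and pitfalls. Because some participants "may not have perfectly healthy non-paretic sides, we will use the data from the healthiest subjects based on their clinical testing", the plan will restrict the data, and the only benefit it names is that the groups may separate more. The wording is unconditional and is not labelled a sensitivity analysis.

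The same paragraph says the authors expect that mean maximum shear strain "will be statistically significant between the healthy (non-paretic) and paretic latent and active PSSP groups to proceed to the R33 phase". It also says "We will have twice as much data for the non-paretic arm than for the latent and active PSSP groups".

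Other parts of the plan contain no selection:

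- Section 4a, study design: "All 40 subjects will also undergo testing on their non-paretic arm which will serve as a proxy for" a healthy control.
- Aim 2, US Data Analysis: shear strain "will be compared for latent and active PSSP on the paretic and non-paretic sides using mixed model analysis, as described above for Aim 1".
- Aim 1, MRI Data Analysis, which supplies that model: the two sides are nested within a person, and "healthy (non-paretic) versus latent PSSP versus active PSSP are examined as fixed effects".
- Section 7 (outcomes and sample size) does not mention a selection.

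The clinical battery is broad ("All clinical assessments will be performed on both arms and be used to correlate with the imaging measures"), and no measure in it is designated for choosing the healthiest participants.

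**The concern.** The selection changes the comparator in the contrasts that the paragraph wants to be significant before R33. If clinically healthier participants also have higher strain on the non-paretic side, keeping only them raises the control mean. The paretic arms then look reduced even when they do not differ from the full set of non-paretic arms. The false positives fall in the hypothesised direction.

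The text also leaves open what is dropped. The 2:1 remark about non-paretic data suggests that only control arms go; the word subjects suggests that both arms go. The two readings have different consequences, and so does the choice of clinical score. The plan therefore conflicts with its own definition of the control, and the direction and size of any bias depend on choices not yet made.

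**Working it through.** **The plan's own figure.** Section 7c says "a sample size of 17 per group is adequate for statistical significance at the 0.05 level with 80% power", for a standardised difference of 1. A two-sided two-sample t test needs 16.7 per group, so 17, with 80.7% power. Allowing 15% attrition, 17 / 0.85 = 20. Both figures reproduce.

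**Inputs.** From the plan: 17 per group (34 completers), level 0.05 (two-sided assumed), and the three-level mixed model. Assumed, because the plan gives no values: correlation r of 0.3 to 0.7 between clinical score and strain; correlation of 0 or 0.5 between a person's two arms; and 90, 75 or 50% kept (31, 26 or 17 of 34). Null: paretic strain equals strain in all non-paretic arms. The score is unrelated to latent or active group.

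**Hand check: only control arms dropped, arms uncorrelated.** Let m be the mean standardised score of those kept (expected order statistics for 34): 0.168, 0.391 and 0.780.

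- False shift in SD = r × m.
- SE = √(1/17 + 1/n kept): 0.302, 0.312 and 0.343.
- Error = P(Z > 1.96 − shift/SE) + P(Z < −1.96 − shift/SE).

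| Controls kept | r | Shift | Shift/SE | Error |
|---|---|---|---|---|
| 31 (90%) | 0.3 | 0.050 | 0.17 | 5.3% |
| 31 (90%) | 0.7 | 0.118 | 0.39 | 6.8% |
| 26 (75%) | 0.3 | 0.117 | 0.38 | 6.6% |
| 26 (75%) | 0.7 | 0.274 | 0.88 | 14.2% |
| 17 (50%) | 0.3 | 0.234 | 0.68 | 10.5% |
| 17 (50%) | 0.7 | 0.546 | 1.59 | 35.6% |

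**Simulation of the planned model** (person random intercept, known variance, 20,000 null studies per setting). Error is per contrast, at 90 / 75 / 50% kept:

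- All arms kept: 5%.
- Only control arms dropped, score tracking non-paretic strain more, or both arms equally: 5–7 / 5–14 / 7–35%. With the variance estimated by REML: 5–8 / 6–16 / 8–40%. Both contrasts falsely significant in the hypothesised direction (known variance): 0.2–1 / 0.4–4 / 1–19%, against 0.1–0.3% with all arms kept.
- Only control arms dropped, score related to non-paretic strain only through paretic strain: about 5%. At r = 0.7 and arm correlation 0.5 the score still correlates 0.7 × 0.5 = 0.35 with non-paretic strain, but the retained paretic arms carry that information and the mixed model adjusts for it.
- Whole participants dropped, score tracking non-paretic strain more: 5–7 / 5–13 / 6–25%.
- Whole participants dropped, score tracking both arms equally: 4–5%, with no shift.
- Whole participants dropped, score tracking paretic strain more: the shift reverses, and errors in the hypothesised direction fall to 0–2% against a nominal 2.5%.

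In every setting the rule is a fixed cut on a clinical score and never looks at the imaging.

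**Latent versus active.** Type I error stays about nominal. If whole participants are dropped evenly across groups, t-test power at a standardised difference of 1 goes from 81% (17+17) to 77% (16+15), 69% (13+13) and 49% (9+8).

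**The case against.** The best defence is that healthy tissue is the intended comparator. Section 4a calls the non-paretic arm a proxy, and impaired controls would pull the contrast towards zero. For that target, restricting the controls serves the question, and calling the shift a type I error depends on the null chosen. This stands in part. A restricted comparison is legitimate if it is defined and labelled as such, but the plan defines no healthy arm and elsewhere uses all 40.

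The scale can also be challenged. The text speaks of only some imperfect sides, which fits modest exclusion, and Section 5 already excludes significant injury to either upper limb and other neurologic disease affecting motor response. Both points favour the 90% and 75% figures. The 35% needs r = 0.7, half the controls dropped and uncorrelated arms. With arm correlation 0.5 the same corner gives about 31% if the score tracks the non-paretic side more, and about 17% if it tracks both equally. Section 7c expects a gain from within-person pairing, which implies positive correlation. When the score tracks both arms equally, the top corner with uncorrelated arms is also nearly degenerate: the two strains would explain 0.49 + 0.49 = 98% of the score.

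A reader might infer three stronger claims that the documents do not support:

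- That the inflation comes from the missing timing or blinding. The figures arise under a fixed, blind rule, and nothing says the choice will follow sight of the imaging. Any added harm from such a choice is not quantified here.
- That any link between clinical status and non-paretic strain is enough. The case at 0.35 shows that it is not.
- That R33 hangs on a formal go/no-go test. The paragraph states an expectation, and no decision rule is set out.

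**Conclusion.** The point holds in a conditional form. The selection conflicts with the control defined in the study design and with the stated mixed model, and no criterion or share kept is given. Error is inflated in the two healthy-versus-paretic contrasts in either of two cases: only control arms are dropped and the score carries information on non-paretic strain beyond paretic strain, or whole participants are dropped by a score that tracks the non-paretic side more. The likelier sizes are modest, with up to about 7% per contrast at 90% kept and 14% at 75% kept. All sizes rest on assumed correlations and shares. The latent-versus-active comparison that sizes the study is not biased in this way, though it loses power if whole participants are removed. This should be fixed before analysis.

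**What to change.** Remove the selection from the primary Aim 2 analysis and from the significance result expected before R33. State that every available non-paretic arm enters the mixed model, as the study design section already implies.

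If a comparison with healthier tissue is wanted, make it one sensitivity analysis. Name the clinical criterion in advance, apply it blind to imaging, and say whether one arm or both are removed. Report it as answering a different question (comparison with selected healthy tissue), and note that it can still shift the contrast even when both arms are dropped together.

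The change is to wording only; it adds no visits, scans or participants. The price is that the paretic-versus-healthy contrast may look smaller and some imperfect non-paretic arms stay in the control set.

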**b. Study duration and number of study visits required of research participants.**

This study is cross-sectional and will take place over two-years. Each participant will come to the lab for three sessions (for clinical assessment, ultrasound and MRI), each of which will take around 3-4 hours.

**c. Definition of treatment failure or participant removal criteria.**

Patients will be advised verbally and in the written ICF that they have the right to withdraw from the study at any time without prejudice or loss of benefits to which they are otherwise entitled. The investigator may discontinue a patient from the study in the event of an intercurrent illness, adverse event, and other reasons concerning the health or well-being of the patient, or in the case of lack of cooperation, non-compliance, protocol violation, or other administrative reasons. If a patient does not return for a scheduled visit, every effort will be made to contact the patient/caregiver. Regardless of the circumstance, every effort will be made to document patient outcome. The investigator / study team will inquire about the reason for withdrawal, and follow-up with the patient/ regarding any unresolved adverse events. If the patient withdraws from the study, no further evaluations will be performed and no additional data will be collected, but vital status will be documented at the end of the study period.

Date: August 28, 2023

Principal Investigator: [name]

Application Number: IRB00354876

**d. Description of what happens to participants receiving therapy when study ends or if a participant's participation in the study ends prematurely.**

The unique identifier key will be retained and will be destroyed two years after the study ends.

**e. If biological materials are involved, please describe all the experimental procedures and analyses in which they will be used.**

Not Applicable

## **5. Inclusion/Exclusion Criteria**

### **Inclusion Criteria**

- 18 years or older
- Hemiparesis from Ischemic or Hemorrhagic Stroke
- 4- 180 months post-stroke with Hemiparesis since the incidence and intensity of PSSP
- Show a difference of more than 10 degrees of passive ER-ROM between non-paretic and paretic shoulders with or without pain
- Able to provide informed consent and comply with testing protocols

### **Exclusion Criteria**

- Received treatment for spasticity with Botulinum Toxin or Intrathecal Baclofen within the past three months
- Have another neurologic condition that may affect motor response (e.g. Parkinson's disease, ALS, MS)
- Have a contraindication to MRI (claustrophobia, magnetic pacemakers and clips)
- Have non-musculoskeletal PSSP such as only central pain or chronic regional pain syndrome (CRPS)
- Have a complicated medical condition, or significant injury to either upper limb.

## **6. Drugs/ Substances/ Devices**

- a. The rationale for choosing the drug and dose or for choosing the device to be used.**
- b. Justification and safety information if FDA approved drugs will be administered for non-FDA approved indications or if doses or routes of administration or participant populations are changed.**
- c. Justification and safety information if non-FDA approved drugs without an IND will be administered.**

There is no drug or device intervention in this observational study.

## **7. Study Statistics**

**a. Primary outcome variable.**

This study has two primary outcomes. The first, which is the primary outcome for AIM 1, is to quantify the extent of HA accumulation using 3-D T1ρ MRI in both arms. The second, which is the primary outcome for AIM 2, is to use Quantitative Shear Stain Mapping to distinguish between latent and active PSSP on the paretic side compared with the non-paretic side.

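### Each aim analyses two muscles and three contrasts at an unadjusted 0.05 with no named primary test, and the Aim 2 progression rule does not say which muscle or whether any or all comparisons must succeed

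*Combined protocol and SAP*

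**What the plan says.** Section 7a: "This study has two primary outcomes". One is the extent of HA accumulation on T1rho MRI (Aim 1); the other is shear strain mapping (Aim 2). Neither is tied to a muscle or to a statistical test.

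Section 4a (study design) images the "pectoralis major (key internal rotator) and infraspinatus (key external rotator) muscles of both arms". The Aim 1 MRI Data Analysis paragraph plans a mixed model with sides nested within person, in which "healthy (non-paretic) versus latent PSSP versus active PSSP are examined as fixed effects". The Aim 2 US Data Analysis paragraph says that shear strain in the two muscles "will be compared for latent and active PSSP on the paretic and non-paretic sides using mixed model analysis, as described above for Aim 1".

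Section 7c sets the sample size "based on the more stringent sample size requirement for Aim 2, which will compare two independent groups", and states that "a sample size of 17 per group is adequate for statistical significance at the 0.05 level with 80% power", taking Cohen's d as 1. It then adds that "we will also have 80% power to detect differences between latent PSSP versus healthy (non-paretic) shoulders and active PSSP versus healthy shoulders".

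On progression, the Aim 2 expected-results paragraph says: "We expect that the mean maximum shear strain will be statistically significant between the healthy (non-paretic) and paretic latent and active PSSP groups", and makes this the condition for moving to the R33 phase. There is no corresponding sentence for Aim 1.

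The documents state no primary muscle, no rule for combining muscles, no testing order, no overall test that must come first, and no multiplicity adjustment.

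**The concern.** A three-level factor gives three pairwise contrasts, and section 7c claims power for each, so they are intended as inferential comparisons. With two muscles and no rule between them, each aim has six tests that could be reported as its primary result. The sample size protects one. If any of the six can be read as meeting the aim, 0.05 is not the error rate of the claim.

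For Aim 2 there is also a decision attached. The progression sentence names healthy versus the two paretic groups, whereas the study is sized on latent versus active. It leaves open the muscle and whether one or both paretic groups must differ from healthy. The error rate of that decision is therefore undefined until someone chooses a reading, and as written the choice could be made after the data are seen.

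**Working it through.** **Inputs.** From the documents: d = 1, alpha 0.05, power 80%, 17 per group, 15% attrition (section 7c); two muscles (section 4a); three levels (Aim 1 and Aim 2 analysis paragraphs). Assumed, because the documents give no values: correlation between sides 0-0.7 and between muscles 0-0.9.

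**The plan's own figure.** For a two-sample t-test, the noncentrality is d·√(n/2). With n = 17 it is √8.5 = 2.92 on 32 degrees of freedom, giving power 80.7% at two-sided 0.05; n = 16 gives 78.1%. So 17 per group reproduces, as a single two-sided test. Enrolment: 17/0.85 = 20. This also reproduces.

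**Upper reference points, if tests were independent.**
- Any of six: 1 − 0.95^6 = 26.5%.
- Either paretic group versus healthy, either muscle (four tests): 1 − 0.95^4 = 18.5%.
- Latent versus active, either muscle (two tests): 1 − 0.95^2 = 9.75%.
- Both paretic groups versus healthy in the same muscle: 0.05² = 0.0025 per muscle, so 1 − (1 − 0.0025)² = 0.5% over two muscles.

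**Allowing for correlation.** Null trials were simulated with two sides and two muscles per person. The contrasts were tested either by one two-sample and two paired t-tests per muscle, or by mixed-model contrasts sharing the pooled non-paretic mean. Results for 17 and 20 per group are similar.

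| Muscle correlation | Any of six, t-tests | Any of six, mixed model |
|---|---|---|
| 0 | about 25%, at most 26% | 22-23% |
| 0.5 | 23-25% | 20-22% |
| 0.9 | 18-19% | 16-17% |

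Over all settings:
- any of six: about 16-26%;
- latent versus active in either muscle: 7-10%;
- either paretic group versus healthy in either muscle: 13-19%;
- both paretic groups versus healthy in the same muscle: about 0.5-1%.

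**Why a later correction is not a substitute.** Bonferroni over six tests (0.05/6) leaves 54.7% power at d = 1 with 17 per group. Restoring 80% takes 27 per group, or 27/0.85 = 32 enrolled.

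**Power of a single named test.** One prespecified muscle: 80.7%, as planned. For the average of two muscles with correlation r, the standardised effect is the mean shift divided by √((1 + r)/2).

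| r | Both muscles shift by 1: effect, power | One muscle shifts by 1: effect, power |
|---|---|---|
| 0.3 | 1.240, 93.9% | 0.620, 41.8% |
| 0.5 | 1.155, 90.4% | 0.577, 37.2% |
| 0.7 | 1.085, 86.6% | 0.542, 33.5% |

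**The case against.** A reader might infer that each aim carries a 21-26% chance of a false decision to proceed. The documents do not support that. The R33 sentence stands under Aim 2 only, and it concerns healthy versus the paretic groups, so latent versus active is not a stated route to success. Its wording joins latent with active; if both must differ from healthy in the same muscle, the chance is about 0.5-1%. A reader might also pool both aims and quote 1 − 0.95^12 = 46%. That assumes twelve independent tests and adjusts across separate aims, which is not the issue here.

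The plan does imply lead contrasts. Section 2 states paretic versus non-paretic for Aim 1 and active versus latent for Aim 2, and section 7c sizes on the latter. If that implied contrast is accepted for Aim 2, the open choice is mainly the muscle, and the relevant figure is 7-10%. The plan also does not say that the muscles are modelled separately or that all pairwise tests will be reported; that is a reading of a brief text. Finally, this is a 40-patient observational phase meant to develop measures, and how much formal gatekeeping it needs is partly a matter of judgement.

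These points narrow the concern but do not remove it. An implied contrast is not a declared primary test, no section chooses a muscle, and the plan itself attaches statistical significance to a progression decision.

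**Conclusion.** The concern holds in limited form. Within each aim the plan permits six tests at 0.05 and names none as primary, so the chance of at least one false positive is about 16-26% under the global null. For latent versus active alone, across the two muscles, it is about 7-10%. For the Aim 2 progression decision the chance depends on how one sentence is read, from about 0.5-1% to 13-19%.

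The ranges rest on the assumed correlations and on no true effect anywhere. They do not count the further freedom, in the Aim 2 text, to restrict the non-paretic data to the clinically healthiest participants.

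**What to change.** In section 7a and in the Aim 1 and Aim 2 analysis paragraphs of section 4a, name one primary test per aim at two-sided 0.05:
- Aim 1: paretic versus non-paretic T1rho.
- Aim 2: active versus latent shear strain, the contrast used for sizing. Say how this relates to the hypothesis in section 2, which is framed relative to the non-paretic side.

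Choose one of two ways to handle the muscles, and write it down before analysis:
- One prespecified muscle (pectoralis major). This keeps about 80% power at d = 1.
- The two-muscle average, from one mixed model with muscle as a within-arm factor. Power is about 87-94% if both muscles shift by d = 1, but about 33-42% if only one does (muscle correlation 0.3-0.7). The documents expect a change in both muscles for T1rho; they make no such statement for shear strain.

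Test the remaining contrasts and the muscle-specific effects in a fixed, written sequence, or label them secondary. For R33, keep the investigators' comparison of healthy with latent and active, and state that both contrasts must be significant in the prespecified muscle or average.

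This costs wording only: no alpha split between aims and no extra patients. There are two downsides. Power is lost for an effect confined to the muscle not chosen, or to one muscle if the average is used. Requiring both R33 contrasts also lowers the chance of a true proceed: taking the plan's conservative 80% for each and treating them as independent, 0.80 × 0.80 = 64%. It would be higher if the two sides are correlated within person, as section 7c expects.
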